## 8.4 Vital signs, physical findings, and other observations related to safety

### 8.4.1 Vital signs, body weight, height, BMI, and head circumference

Vital signs (systolic BP [SBP], diastolic BP [DBP], and pulse rate) will be assessed after at least 3 minutes at rest in a supine position throughout the study, according to the tabular schedules of procedures. Body weight, height, and head circumference will also be assessed throughout the study, according to the tabular schedules of procedures.

Assessment of orthostatic changes (only in ambulatory subjects) will also be performed as follows: after the 3 minute measurement in supine position, the subject is asked to stand up, and SBP, DBP and pulse rate are taken approximately 1 minute and approximately 3 minutes after the subject stands up, as feasible.

Observed values of SBP, DBP, pulse rate, body weight, height, BMI, and head circumference will be summarized for each visit and Last Visit. Change from Baseline for SBP, DBP, pulse rate, body weight, height, BMI, and head circumference will be summarized for all post-Baseline visits, and Last Visit.

Orthostatic changes of SBP, DBP, and pulse rate will be summarized for each visit and Last Visit.

Markedly abnormal (MA) values are defined as those MA values during the defined Treatment Period at scheduled or unscheduled visits which occur on or after the first EP0034 LCM administration through to the end of the study. The age at the time of assessment will be used for determining MA (as defined in Section 3.2.24).

The number and percentage of subjects with a MA value, MA low value, and MA high value, at each post-Baseline visit and Last Visit, for which SBP, DBP, pulse rate, and body weight are scheduled to be assessed, and Last Visit, will be presented. Percentages will be relative to the number of subjects with a value at each time point.

The abnormal vital sign criteria are defined as follows:

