5.1.1 Study duration per subject

The maximum duration of LCM administration during EP0034 will be approximately 2 years.

The start of the study is defined as the first visit of the first subject entering the study. The end of the study is defined as the date of the last telephone contact (or last site visit if telephone contact does not happen) of the last subject in the study.

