6 SELECTION AND WITHDRAWAL OF SUBJECTS

6.1 Inclusion criteria

To be eligible to participate in this study, all of the following criteria must be met:

1. An Institutional Review Board (IRB)/Independent Ethics Committee (IEC) approved written Informed Consent form (ICF) is signed and dated by the subject or legal representative. The ICF or a specific Assent form, where required, will be signed and dated by minors.
2. Subject has completed the Transition Period of SP0967 or SP0969 for the treatment of uncontrolled partial-onset seizures in pediatric epilepsy.
3. Subject is expected to benefit from participation, in the opinion of the investigator.
4. Subject/legal representative is considered reliable and capable of adhering to the protocol (eg, able to understand and complete diaries), visit schedule, and medication intake according to the judgment of the investigator.
5. Subject is male or female aged 1 month to ≤ 17 years.
6. Subject has a diagnosis of epilepsy with partial-onset seizures.

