## 3 DATA ANALYSIS CONSIDERATIONS

### 3.1 General presentation of summaries and analyses

Statistical analysis and generation of tables, figures, subject data listings, and statistical output will be performed using SAS Version 9.1 or higher. All tables and listings will use Courier New font size 9.

Descriptive statistics will be displayed to provide an overview of the study results. For categorical parameters, the number and percentage of subjects in each category will be presented. The denominator for percentages will be based on the number of subjects appropriate for the purpose of analysis. Unless otherwise noted, all percentages will be displayed to 1 decimal place. No percentage will be displayed for zero counts, and no decimal will be presented when the percentage is 100%. For continuous parameters, descriptive statistics will include number of subjects (n), mean, standard deviation (SD), median, minimum, and maximum.

Decimal places for descriptive statistics will always apply the following rules:

- “n” will be an integer
- Mean, SD, and median will use 1 additional decimal place compared to the original data
- Minimum and maximum will have the same number of decimal places as the original value

All summaries, unless otherwise stated below, will be presented overall for all subjects and additionally based on the subject’s age at time of entry into study EP0034, using the following age groups:

- $\geq 1$  month to  $< 4$  years
- $\geq 4$  to  $< 18$  years

Summaries for PedsQL will be presented overall for all applicable subjects and additionally based on the subject’s age at Baseline (using the Baseline definition in [Section 3.3](#)), using the following age groups:

- $\geq 1$  month to  $\leq 12$  months
- $> 12$  months to  $\leq 24$  months
- $> 2$  years to  $\leq 4$  years
- $\geq 5$  to  $\leq 7$  years
- $\geq 8$  to  $\leq 12$  years
- $\geq 13$  to  $\leq 18$  years
- Total  $\geq 5$  years to  $\leq 18$  years

Summaries for CBCL/1½-5 will be presented overall for all applicable subjects and additionally based on the subject’s age at time of entry into study EP0034, using the following age groups:

- $\geq 18$  months to  $< 2$  years

- $\geq 2$  to  $< 4$  years
- Total  $< 4$  years
- $\geq 4$  to  $< 6$  years

Summaries for CBCL 6-18 will be presented overall for all applicable subjects and additionally based on the subject's age at time of entry into study EP0034, using the following age groups:

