### 3.3 Definition of Baseline values

In general, Baseline will be defined as the last non-missing value collected prior to the first dose of LCM in the previous pediatric studies for efficacy and safety variables, unless otherwise noted for a specific type of data.

The Baseline value for seizure counts (only applicable for subjects from SP0969) will be taken from the subject diary completed during the 8-week Baseline Period before receiving LCM in study SP0969.

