**Table 8–1: Vital signs abnormality criteria**

Parameter	Age Range	Abnormality Criteria
	3y - <12y	<60 >130
	12y - <17y	≤50 >120
	≥17y	≤50 and a decrease from Baseline of ≥15 >120 and an increase from Baseline of ≥15
Systolic Blood Pressure (mmHg)	<6m	<60 >100
	6m - <3y	<70 >120
	3y - <12y	<80 >140
	12y - <17y	<90 >160
	≥17y	≤90 and a decrease from Baseline of ≥20 >180 and an increase from Baseline of >20
Diastolic Blood Pressure (mmHg)	<6m	<40 >65
	6m - <3y	<45 >75
	3y - <12y	<50 >80
	12y - <17y	≤50 >105
	≥17y	≤50 and a decrease from Baseline of ≥15 >105 and an increase from Baseline of ≥15
Temperature	>1m	>101 °F (38.3 °C)
Body Weight	1m - <17y	<3% or >97% of the normal body weight growth curve ranges a based on gender and the age of subject on date of weight assessment
	≥17y	≥10% change from Baseline (an increase or a decrease)

Abbreviations: m=months, y=years. A month is defined as 28 days; a year is defined as 365.25 days.

a Source: <http://www.cdc.gov/growthcharts/>.

A subject data listing of all vital signs for study subjects with an AE mapped to the PT bradycardia or sinus bradycardia will be presented.

A subject data listing of all vital signs values including body weight, height, BMI, and head circumference for all subjects will be presented. A separate listing including MA vital signs values will also be presented.

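### Height, BMI and head circumference are summarized only as raw values and raw change, and weight adds only an extreme-value count, so the growth tables cannot show whether growth was normal or slowed

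*SAP*

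**What the plan says.** - **Growth summaries (SAP 8.4.1).** "Change from Baseline for SBP, DBP, pulse rate, body weight, height, BMI, and head circumference will be summarized for all post-Baseline visits"; Last Visit is included, and observed values are tabulated in the same way. No z-score, centile or velocity is planned for height, BMI or head circumference.
- **Age bands (SAP 3.1).** Default summaries are overall and by the subject's "age at time of entry into study EP0034, using the following age groups": 1 month to under 4 years, and 4 to under 18 years.
- **Baseline (SAP 3.3).** In general, "Baseline will be defined as the last non-missing value collected prior to the first dose of LCM in the previous pediatric studies".
- **Weight (SAP Table 8–1).** Under 17 years, a value is markedly abnormal at "<3% or >97% of the normal body weight growth curve ranges", judged by gender and age at the measurement. From 17 years the rule is a change of at least 10% from Baseline in either direction. SAP 8.4.1 tabulates low and high counts at each post-Baseline visit and Last Visit. Height, BMI and head circumference have no criterion.
- **New onset.** The SAP 8.4.1 definition of a markedly abnormal value does not require a normal Baseline. The laboratory definition in SAP 8.3 does.
- **Other growth output.** A table of growth-related TEAEs identified by medical review (SAP 8.2), a Tanner stage shift table by gender (SAP 8.4.6) and subject listings (SAP 8.4.1).
- **Comparator.** None: the study is open-label and not randomized (SAP 3.6).

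**The concern.** For blood pressure, a mean change near zero is a sensible picture of no effect. For height or head circumference in a child it is not. A healthy child gains, and the size of the gain depends on age, sex and elapsed time. Each planned age band mixes very different growth phases. Baseline predates EP0034, so the change covers more than time in this study. Only subjects with a measurement contribute at a visit, so the age mix can move as subjects leave.

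Without a control arm, an external age and sex reference is the only benchmark for expected growth. The plan uses one for weight, in a limited form, and not for the other three measures. At stake is whether about two years of growth data in children can be read at all. Long-term safety is the primary objective, and body weight and height are named among the other safety variables (Protocol 4.1.2).

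**Working it through.** The plan states no growth figure, so there is none to reproduce. The check has three parts.

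**1. Does any planned output give a no-effect value for mean raw change?** The by-visit tables give none, because expected growth differs by age and sex within each band. The TEAE table depends on events being reported. Tanner stage is assessed only in pubescent subjects. Listings show values without a reference. The weight count is referenced, but only at the extremes.

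**2. How large is the ambiguity for height? (illustration)** The velocities are assumed, not taken from the documents, and are spread uniformly within a band. Time is 96 × 7 / 365.25 = 1.84 years, from EP0034 entry to the last scheduled Treatment Period visit. The interval from the SAP Baseline is longer, by an amount the documents do not give.

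- Mean gain with no effect = midpoint × 1.84
- SD from age mix alone = (range / √12) × 1.84
- Width = movement in the no-effect mean when average velocity moves between the quartile points of the assumed range = (range / 2) × 1.84

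| Band, assumed cm/year | Mean gain (cm) | SD (cm) | Quartile-point means (cm) | Width (cm) | 10% deficit (cm) | 20% deficit (cm) |
|---|---|---|---|---|---|---|
| Younger, 7–12 | 17.5 | 2.7 | 15.2–19.8 | 4.6 | 1.7 | 3.5 |
| Younger, 6–20 | 23.9 | 7.4 | 17.5–30.4 | 12.9 | 2.4 | 4.8 |
| Older, 4–7 | 10.1 | 1.6 | 8.7–11.5 | 2.8 | 1.0 | 2.0 |
| Older, 1–9 | 9.2 | 4.2 | 5.5–12.9 | 7.4 | 0.9 | 1.8 |

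The ratio of deficit to width does not depend on the interval, because both scale with time. For a 10% deficit it is 0.95/2.5, 1.3/7, 0.55/1.5 and 0.5/4, that is 0.38, 0.19, 0.37 and 0.13. A modest deficit in mean raw change therefore cannot be told from a difference in age mix.

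**3. What does the weight count show?** Read the 3% limit as the 3rd centile, and assume that subjects follow the reference distribution at Baseline with SD 1. If mean z falls by d, the share below the limit is Φ(−1.881 + d).

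- d = 0: 3.0%, or 15 of 500
- d = 0.25: 5.1%, or 26 of 500
- d = 0.5: 8.4%, or 42 of 500

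The 500 is the approximate number eligible (SAP 2.4). A mean shift thus appears only through the tail. A child who moves from the 60th to the 10th centile is never counted, while a child below the limit before LCM counts at every visit measured there. From age 17, a subject who weighed 50 kg at Baseline is flagged on gaining 5 kg, which ordinary growth since the earlier study could produce. On a z-score scale, the no-effect reference for mean change is about 0 at every age.

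**The case against.** The strongest reply is that the plan does what it promised. Protocol 12.3 calls for a descriptive analysis of height and body weight, overall and by visit, and SAP 8.4.1 delivers it. The primary safety variables are TEAE incidences. BMI and head circumference are not named in either list of study variables. Weight already has a gender- and age-referenced count, and growth-related TEAEs, endocrinology summaries and Tanner shifts are also planned. All of this stands. It limits the point to an improvement in interpretability; no stated analysis fails. None of these outputs, however, supplies an expected value for height, BMI or head circumference.

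A reader might infer that normal growth hides any drug effect. The documents do not support that. Under the assumptions above, a 20% deficit is 0.43 to 1.32 of the age-mix SD. Scatter is not the main obstacle either: with the largest older-band SD, 100 subjects give a standard error from age mix of 4.2 / √100 = 0.42 cm. What is missing is the reference mean.

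A reader might also expect z-scores to isolate the effect of LCM. They cannot: there is no control arm, and concomitant AEDs may be added or withdrawn (Protocol 7.8.1).

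**Conclusion.** The point holds in a limited form. Height, BMI and head circumference have no age- and sex-standardized summary. Weight has one only as an extreme-value count that is not restricted to new onset and changes to a raw rule at 17. Mean raw change over two wide age bands, from a Baseline in an earlier study and with no comparator, cannot show whether growth was normal or slowed.

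The size cannot be derived from the documents. The illustration puts a 10% height deficit at 13% to 38% of the movement that age mix alone could cause. This rests on assumed velocity ranges, uniform within each band. The structural conclusion does not depend on those figures.

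It would go too far to say that weight is summarized only as raw change, or that every effect would be missed. The addition is worth making because it is cheap; the primary safety analysis is unaffected.

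**What to change.** - Keep the observed-value and raw-change summaries in SAP 8.4.1, which Protocol 12.3 requires for height and weight.
- Add age- and sex-specific z-scores for weight, height, BMI and head circumference from the growth-chart source cited under Table 8–1, at the ages that source covers. The documents do not show its coverage, so the SAP should state the ages used for each measure.
- Use age at assessment from SAP 3.2.24, and state how age is derived at the Baseline date in the previous study.
- Summarize observed z-score and change in z-score from Baseline by visit and Last Visit.
- Add a Baseline-to-Last-Visit shift table by centile category. This separates new low or high values from those present before LCM, much as the SAP already does with T-score categories for CBCL and BRIEF.
- State that the results are read against the reference population, not as an isolated drug effect.

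The cost is extra programming and tables; no new data are needed. Z-scores will be less precise for infants with incomplete birth dates, because SAP 3.2.24 then starts from enrollment age in years. Those subjects should be identified in the listing.

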### 8.3 Clinical laboratory evaluations

Hematology, blood chemistry (including liver function tests), urinalysis, and endocrinology parameters are assessed throughout the study, according to the tabular schedules of study procedures. Urinalysis will be performed for subjects  $\geq 5$  years of age only.

All summaries of laboratory parameters will only summarize parameters planned based on the protocol. However, both planned and unplanned laboratory parameters will be provided in subject data listings. Summaries will include hematology, chemistry and endocrinology results; urinalysis results will be included in subject data listings only.

Observed values of hematology, chemistry, and non-gender specific endocrinology parameters (ie, thyroid stimulating hormone, triiodothyronine [total and serum-free], and thyroxine [total and serum-free]) will be summarized for each visit and Last Visit. Change from Baseline for hematology, chemistry, and non-gender specific endocrinology parameters will be summarized for all post-Baseline visits, and Last Visit. Gender specific endocrinology parameters (ie, follicle stimulating hormone, luteinizing hormone, and testosterone) will be presented similarly, by gender.

A shift table that cross-tabulates Baseline versus maximum result during the Treatment Period in categories of  $<1 \times$  ULN (upper limit of normal),  $1$  to  $<2 \times$  ULN,  $2$  to  $<3 \times$  ULN,  $\geq 3 \times$  ULN, and missing will be presented for liver function tests (LFT) which include ALT, AST, GGT, Total Bilirubin, and ALP.

Treatment-emergent markedly abnormal (TEMA) values are defined as those TEMA values during the defined Treatment Period at scheduled or unscheduled visits which occur on or after the first EP0034 LCM administration through to the end of the study but were normal at Baseline. The age at the time of assessment will be used for determining TEMA (as defined in Section 3.2.24).

The number and percentage of subjects with a TEMA value, TEMA low value, and TEMA high value will be summarized, at each post-Baseline visit and Last Visit. Percentages will be relative to the number of subjects with a value at each time point. Criteria for determining if a value is TEMA are detailed in Appendix 12.1.

Serum and urine pregnancy testing will be performed on all females of childbearing potential, according to the tabular schedules of study procedures.

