#### 8.4.2 Electrocardiograms (ECGs)

Standard 12-lead ECGs (2 interpretable recordings [20 to 30 minutes apart]) will be performed throughout the study, according to the tabular schedules of procedures.

For ECGs, Baseline will be defined as the average of all pre-dose interpretable readings. For all post-Baseline visits, the average of all interpretable readings at the specified visit will be used for summaries.

Observed values of ECG results will be summarized for each visit and Last Visit. Change from Baseline in ECG results will be summarized for all post-Baseline visits, and Last Visit. This will be summarized overall and repeated by weight band using the levels defined in [Section 3.2.10](#).

The number and percentage of subjects with no abnormality, an abnormal but not clinically significant finding, and a clinically significant finding, will be summarized for all visits, and Last Visit. Percentages will be relative to the number of subjects with an ECG assessment at each visit. Subjects are counted at most once at each visit based on the worst observed outcome across all abnormalities reported at that visit.

Summaries of shifts from Baseline to post-Baseline visits, and from Baseline to Last Visit will also be provided based on the categories normal, abnormal, not clinically significant, and abnormal, clinically significant.

A listing of ECG data will be provided for all subjects with other significant TEAEs in the Cardiac and ECG Related Terms category defined in [Appendix 12.2](#). A subject data listing of all ECG parameter values for all subjects will also be presented. Listings will include results from each recording and the average of all recordings.

The number and percentage of subjects with treatment-emergent ECG abnormalities will be presented for each post-Baseline visit and Last Visit. Abnormalities reported at an unscheduled visit will be summarized under the scheduled visit preceding the unscheduled visit (if the abnormality was not present already at the preceding scheduled visit). Treatment-emergent is defined as meeting the criteria at any post-Baseline visit during the Treatment Period (including unscheduled visits) and not meeting the same criteria during Baseline. The age at the time of visit/assessment will be used for determining abnormality criteria (as defined in [Section 3.2.24](#)). All ECG parameter values will be listed for subjects meeting any abnormality criteria.

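### Below age 17, markedly abnormal blood pressure and pulse are counted without reference to Baseline, so the per-visit table cannot separate pre-existing from new threshold crossings; the gap is mainly for blood pressure

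*SAP*

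**What the plan says.** SAP 8.4.1 defines vital-sign abnormality by period: "Markedly abnormal (MA) values are defined as those MA values during the defined Treatment Period at scheduled or unscheduled visits". The sentence goes on "which occur on or after the first EP0034 LCM administration through to the end of the study. The age at the time of assessment", so it closes on the time window and moves to age. It sets no condition on the Baseline value. The number and percentage of subjects with an MA, MA low and MA high value are tabulated at each post-Baseline visit and at Last Visit, over all subjects with a value at that time point.

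Table 8-1 uses fixed limits for pulse, systolic (SBP) and diastolic (DBP) pressure in all four age bands below 17 years. Only the rows for 17 and over add a change, for example a low pulse defined as "≤50 and a decrease from Baseline of ≥15".

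Two neighbouring sections work differently. The laboratory sentence in SAP 8.3 uses the same time window but ends "through to the end of the study but were normal at Baseline". SAP 8.4.2 counts an ECG abnormality as treatment-emergent only if the subject was "not meeting the same criteria during Baseline".

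Baseline exists for this purpose. SAP 3.3 states that "Baseline will be defined as the last non-missing value collected prior to the first dose of LCM in the previous pediatric studies", and change from Baseline in SBP, DBP and pulse is already planned.

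**The concern.** Protocol 6.1 admits subjects from 1 month to 17 years of age, so nearly all enter in rows with no Baseline condition. A child who sits naturally beyond a limit can be counted at visit after visit with no change at all, and the table gives no Baseline figure to set against that count.

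The study has one arm and its primary objective is long-term safety. With no control group, the subject's own value before lacosamide is the only reference. Protocol 12.3 says shift tables may be used. The SAP plans them for liver tests, ECG, the complete neurological examination, Tanner stage and the behaviour scales, but not for vital signs. A reader of the blood-pressure table cannot tell how much of each percentage was there before treatment, and a real shift would be diluted by children who never changed.

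**Working it through.** The plan has no figure to reproduce here: the study is descriptive and has no formal sample-size calculation. The check has two parts.

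**1. The rule applied to unchanged values.** Each case has the same value at Baseline and on treatment.

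| Parameter, age | Value | Table 8-1 limit | Counted as MA? | Counted if Baseline must not meet the limit? |
|---|---|---|---|---|
| DBP, 8 y | 48 | <50 or >80 | Yes | No |
| DBP, 8 y | 84 | <50 or >80 | Yes | No |
| DBP, 14 y | 50 | ≤50 or >105 | Yes | No |
| Pulse, 8 y | 135 | <60 or >130 | Yes | No |
| DBP, 17 y | 50 | ≤50 and a fall of ≥15 | No | No |
| Pulse, 17 y | 125 | >120 and a rise of ≥15 | No | No |

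Below 17 the unchanged value is counted. At 17 it is not.

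**2. Size under no drug effect.** The inputs are assumptions, because the documents give neither figure: a proportion *p* of children beyond a limit at any time point (2.5%, 5%, 10%), and a correlation *ρ* between Baseline and a visit (0.3, 0.5, 0.7), with normally distributed values.

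- Probability beyond the limit at both times: P11 = Φ₂(z, z; ρ), with z = Φ⁻¹(p).
- Share of a visit's flags from children already beyond the limit at Baseline: P11 / p.
- Percentage at a visit among children not beyond it at Baseline: (p − P11) / (1 − p).

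Middle case, p = 0.05 and ρ = 0.5: P11 = 0.0122. The share is 0.0122 / 0.05 = 24%. The conditioned percentage is (0.05 − 0.0122) / 0.95 = 4.0%.

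| p (planned table) | ρ | P11 | Share of flags | Conditioned percentage |
|---|---|---|---|---|
| 2.5% | 0.3 | 0.0024 | 10% | 2.3% |
| 2.5% | 0.7 | 0.0083 | 33% | 1.7% |
| 5% | 0.3 | 0.0071 | 14% | 4.5% |
| 5% | 0.5 | 0.0122 | 24% | 4.0% |
| 5% | 0.7 | 0.0196 | 39% | 3.2% |
| 10% | 0.3 | 0.0216 | 22% | 8.7% |
| 10% | 0.7 | 0.0468 | 47% | 5.9% |

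For scale, if all of the approximately 500 eligible subjects had a value at a visit and were below 17, the middle case gives 500 × 0.05 = 25 flagged. About 500 × 0.0122 = 6 of them were already beyond the limit at Baseline. The other 19 come from 475 children, which is 4.0%.

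**The case against.** The strongest reply is that nothing here is an error. The SAP uses two terms, MA and TEMA. It calls the vital-sign values MA and never treatment-emergent, and Protocol 12.3 asks only for a descriptive summary of markedly abnormal values. That stands: a reader might infer that the table mislabels old values as emergent, and the documents do not support that.

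For pulse, a Baseline-conditioned count is largely there already. The heart-rate limits in Table 8-2 equal the Table 8-1 pulse limits in every band below 12 years. From 12 years the ECG limits are <50 or >120, against ≤50 or >120 for pulse at 12 to <17, and SAP 8.4.2 requires the criterion not to be met at Baseline. ECGs are scheduled at five visits after Visit 1 (Weeks 4, 28, 52, 72 and 96), whereas pulse is taken at all twelve. This also stands, and it leaves SBP and DBP as the main gap.

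Other outputs soften the consequence: change from Baseline at every visit, orthostatic changes, full listings, and bradycardia and syncope terms among the other significant TEAEs. None of them counts new blood-pressure crossings.

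A reader might also be drawn to a larger figure. In the same model, a child beyond a limit at Baseline is flagged at one or more of the twelve later visits with probability 56–92%. No planned row pools visits in that way, so that figure does not describe the planned table. Nor would conditioning on Baseline remove the background: 53–90% of no-effect flags come from children who were within the limit at Baseline.

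**Conclusion.** The point holds as a limit on interpretation. Below 17, the per-visit MA table for SBP, DBP and pulse cannot separate pre-existing from new crossings, and nothing else in the plan supplies that count for blood pressure. For pulse, the ECG heart-rate table covers much of it.

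The size is moderate and rests wholly on assumed inputs: about 10–47% of flags come from children already MA at Baseline. The tabulated percentage moves from 5.0% to about 4.0% in the middle case, from 2.5% to 1.7–2.3% at the low end, and from 10% to 5.9–8.7% at the high end. Nothing is hypothesis-tested, so no formal conclusion depends on it. This is a cheap improvement to a safety table, not a correction of a contradiction.

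**What to change.** Keep the planned MA rows and the MA listing, and add to SAP 8.4.1 for SBP, DBP and pulse:

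- A row with the number of subjects MA low and MA high at Baseline.
- A treatment-emergent MA count by direction, for subjects below 17 who did not meet the limit in the same direction at Baseline. The denominator is those subjects with a value at the visit.
- Baseline judged by the age band at Baseline. An unchanged value that becomes MA only because the child enters a new band is not counted as new, and the SAP should say what counts as unchanged. For example, a pulse of 140 is not MA at 2.9 years but is at 3.1 years, and an SBP of 85 is not MA just before 12 years but is just after.
- Subjects with a missing Baseline reported separately.

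The new count should stand beside the existing one and not replace it. An 8-year-old whose DBP falls from 49 to 35 was already below 50 at Baseline and would never enter the treatment-emergent count. Such a child stays visible only in the retained MA rows, the change-from-Baseline summaries and the listing.

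The cost is SAP wording, a few extra rows, and denominators that differ by direction. No new data are needed.
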